#### Grading of Adverse Events

1	Mild	Symptom barely noticeable to subject; does not influence performance or functioning. Prescription drug not ordinarily needed for relief of symptom but may be given because of personality of subject.
2	Moderate	Symptom of a sufficient severity to make subject uncomfortable; performance of daily activities influenced; subject is able to continue in study; treatment for symptom may be needed.
3	Severe	Symptom causes severe discomfort. May be of such severity that subject cannot continue. Severity may cause cessation of treatment with test drug; treatment for symptom may be given and/or subject hospitalized.
4	Life-threatening	Symptom(s) place the patient at immediate risk of death from the reaction as it occurred; it does not include a reaction that, had it occurred in a more serious form, might have caused death.

#### Attribution of Adverse Events

1	Not related	This category applies to those adverse events which, after careful consideration, are clearly and incontrovertibly due to extraneous causes (disease, environment, etc.)
2	Unlikely (must have two)	In general, this category can be considered applicable to those adverse events which, after careful medical consideration at the time they are evaluated, are judged to be unrelated to the test drug. An adverse event may be considered unlikely if or when: 
 
1. It does not follow a reasonable temporal sequence from administration of the test drug.
 
2. It could readily have been produced by the subject's clinical state, environmental or toxic factors, or other modes of therapy administered to the subject.
 
3. It does not follow a known pattern of response to the test drug.
 
4. It does not reappear or worsen when the drug is re-administered.
 

3	Possibly (must have two)	
This category applies to those adverse events for which, after careful medical consideration at the time they are evaluated, a connection with the test drug administration appears unlikely but cannot be ruled out with certainty. An adverse event may be considered possibly related if or when:
 
 
1. It follows a reasonable temporal sequence from administration of the test drug.
 
2. It could not readily have been produced by the subject's clinical state, environmental or toxic factors, or other modes of therapy administered to the subject.
 
3. It follows a known pattern of response to the test drug.
 

4	Probably (must have three)	
This category applies to those adverse events for which, after careful medical consideration at the time they are evaluated, are felt with a high degree of certainty to be related to the test drug. An adverse event may be considered probably related if or when:
 
 
1. It follows a reasonable temporal sequence from administration of the test drug.
 
2. It could not be reasonably explained by the known characteristics of the subject's clinical state, environmental or toxic factors, or other modes of therapy administered to the subject.
 
3. It disappears or decreases on cessation or reduction in dose. There are important exceptions when an adverse event does not disappear upon discontinuation of the drug, yet drug-relatedness clearly exists (e.g., bone marrow depression, fixed drug eruptions, tardive dyskinesia).
 
4. It follows a known pattern of response to the test drug.
 

5	Definitely (must have all)	
This category applies to those adverse events which, the Investigator feels are incontrovertibly related to test drug. An adverse event may be assigned an attribution of definitely related if or when:
 
 
1. It follows a reasonable temporal sequence from administration of the test drug.
 
2. It could not be reasonably explained by the known characteristics of the subject's clinical state, environmental or toxic factors, or other modes of therapy administered to the subject.
 
3. It disappears or decreases on cessation or reduction in dose with re-exposure to drug. (Note: this is not to be construed as requiring re-exposure of the subject, however, a category of definitely related can only be used when a recurrence is observed.)
 
4. It follows a known pattern of response to the test drug.
 

---	---	---

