### **11.3 Relationship to Investigational Product**

It is a regulatory requirement for investigators to assess relationship to investigational product based on information available. The assessment should be reviewed on receipt of any new information and amended if necessary. “A reasonable possibility” is meant to convey that there are facts/evidence or arguments to suggest a causal relationship.

Facts/evidence or arguments that may support “a reasonable possibility” include, e.g., a temporal relationship, a pharmacologically-predicted event, or positive dechallenge or rechallenge. Confounding factors, such as concomitant medication, a concurrent illness, or relevant medical history, should also be considered.

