### **11.5 Disease-Related Events and/or Disease-Related Outcomes Not Qualifying as SAEs**

During the study period, the following conditions will not qualify as an AE or SAE provided they are not considered attributable to study medication:

- Cases of disease progression.
- New or worsened cytopenias even if they result in treatment, and/or hospital admissions.
- Serious infections including neutropenic fever/neutropenic sepsis, line-infection, PCP pneumonia, Clostridium difficile infection
- Neutropenic fever/neutropenic sepsis

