### **FDA Reporting**

All SAEs that are unexpected (i.e., not in the current PROMACTA™ (Eltrombopag) package inserts or the Investigator Brochures) and associated with use of the study drug must be reported to FDA within 15 calendar days, or within 7 calendar days if the SAE was fatal or life-threatening. Novartis will be responsible for FDA reporting of all necessary SAEs.

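### The criterion counts in the 11.1 attribution table conflict with the reasonable-possibility standard in 11.3: a novel event that chemotherapy could also explain scores Unlikely despite positive dechallenge and rechallenge

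*Combined protocol and SAP*

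**What the plan says.** Section 8.2 has the treating team record each adverse event as definite, probable, possible, unlikely or unrelated. The table headed Attribution of Adverse Events in section 11.1 sets a criterion count for four of these five levels.

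- The entry that opens "Unlikely (must have two" lists four criteria. Two of them are "It could readily have been produced by the subject's clinical state, environmental or toxic factors, or other modes of therapy administered to the subject" and "It does not follow a known pattern of response to the test drug". The other two are implausible timing and no recurrence or worsening on re-administration.
- The entry that opens "Possibly (must have two" lists three: plausible timing, "It could not readily have been produced by the subject's clinical state, environmental or toxic factors" or by other therapy, and a known pattern. Dechallenge and rechallenge are absent from it.
- *Probably* needs three of four: timing, no reasonable alternative explanation, dechallenge, known pattern.
- *Definitely* needs all four of these, with recurrence on re-exposure added to the dechallenge criterion.

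Section 11.3 sets a different standard, a reasonable possibility, which may be supported by evidence such as "a temporal relationship, a pharmacologically-predicted event, or positive dechallenge or rechallenge". Confounding factors are to be weighed as well. The protocol does not say how the two sections relate.

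Section 11.5 keeps progression, cytopenias and serious infections out of AE and SAE reporting "provided they are not considered attributable to study medication". The FDA Reporting paragraph covers SAEs that are unexpected "and associated with use of the study drug must be reported to FDA within 15 calendar days". Neither says which levels of the table meet its condition.

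**The concern.** Every patient has just had 7+3 induction, with a planned gap of 7 to 9 days before eltrombopag (4.1), and receives full supportive care (5.9). A ready alternative explanation will therefore often be available. Section 6.1 says safety is not established in chemotherapy-induced thrombocytopenia or AML, so events without a known pattern are ones this trial is well placed to detect. An event with both features counts twice towards *Unlikely*. The evidence that best separates a drug effect from background, namely abatement off drug and recurrence on it, earns nothing under *Possibly*.

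Several things depend on the recorded level:

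- the incidence of eltrombopag-related adverse events, a secondary objective in 2.2;
- the exemptions in 11.5;
- the duty under 11.7 to report SAEs that come to light after eltrombopag has stopped, which applies to those judged related or possibly related;
- the 11.7 rule that treatment-related AEs are followed to resolution or stabilization.

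**Working it through.** No sample size or power figure is involved, and the plan states no number to reproduce. The check applies the table's own counts.

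**Coding (1 = yes, 0 = no).** T: plausible timing. A: ready alternative cause. K: known pattern. D: positive dechallenge. N: drug re-administered and event did not recur.

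**Scores**
- *Unlikely* = (1 − T) + A + (1 − K) + N, met at 2 or more of 4
- *Possibly* = T + (1 − A) + K, met at 2 or more of 3
- *Probably* = T + (1 − A) + D + K, met at 3 or more of 4
- *Definitely*: T, no alternative cause, D with recurrence on re-exposure, and K, all required

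**The profile at issue:** T = 1, A = 1, K = 0, D = 1, rechallenge positive (N = 0).
- *Unlikely* = 0 + 1 + 1 + 0 = 2 of 4: met
- *Possibly* = 1 + 0 + 0 = 1 of 3: not met
- *Probably* = 1 + 0 + 1 + 0 = 2 of 4: not met
- *Definitely*: fails on alternative cause and on known pattern

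**All profiles with plausible timing.** Crossing A (2) × K (2) × D (2) × rechallenge positive, negative or not done (3) gives 24 profiles, 6 per cell.

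| Alternative cause | Known pattern | Profiles reaching *Possibly* or higher |
|---|---|---|
| yes | no | 0 of 6 |
| yes | yes | 6 of 6 |
| no | no | 6 of 6 |
| no | yes | 6 of 6 |

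The failure is confined to one cell, and within that cell dechallenge and rechallenge make no difference. Counting the re-administration criterion as met when the drug was never restarted gives the same 0 of 6.

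**Sensitivity to wording.** *Unlikely* and *Possibly* ask whether another cause could readily have produced the event. *Probably* asks whether another cause reasonably explains it. If the answers are yes and no respectively, then with K = 0 and D = 1, *Probably* = 1 + 1 + 1 + 0 = 3 of 4 (met), *Unlikely* = 2 of 4 (also met) and *Possibly* = 1 of 3 (not met). The event then qualifies for *Probably* and *Unlikely* but not for the level between them, so the scale is not ordered.

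**Against 11.3.** In the profile at issue, timing, dechallenge and rechallenge are all positive, and 11.3 names each as possible support for relatedness. The table credits timing once under *Possibly*, gives the other two nothing there, and leaves *Unlikely* as the only counted level open.

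**The case against.** The strongest reply is that the table does not control safety reporting. The FDA Reporting paragraph names no attribution level. Section 11.3 is where the protocol describes the regulatory relatedness assessment. Section 11.7 sends every SAE to Novartis inside 24 hours whatever its attribution, and Novartis makes the FDA reports. This stands. A reader might infer that expedited reporting of unexpected related SAEs can almost never be triggered; the documents do not support that. Nor do they define unexpected (absent from the package insert or brochure) as having no known pattern, and well-timed events with no known pattern and no ready alternative cause reach *Possibly* in 6 of 6 profiles. The 24-hour route covers only what is recorded as an SAE, however. Events exempted under 11.5, or under 11.4 as linked to disease or induction, may not enter it.

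Second, the wording is partly permissive: an event may be considered unlikely, after medical judgement. That softens the rule but does not cancel a heading that says two criteria must be present. Likewise, 11.3 permits a finding of relatedness and asks that confounders be weighed; it does not compel one. The conflict is that the table's counts exclude a conclusion that 11.3 allows.

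Third, an event that abates off eltrombopag and returns on it is hard to call readily explained by an earlier chemotherapy course. That is fair, but infection, cytopenia and concurrent drugs also count as alternatives, and the table does not tell assessors to revise that answer in light of rechallenge.

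Fourth, a reader might infer that the related-AE rate is pushed towards zero. It is not. An event with plausible timing and a known pattern reaches *Possibly* even when chemotherapy could explain it, so the hepatic and thrombotic effects described in 6.2 and 6.3 can still be attributed. Sections 10.2 and 12.0 also assess adverse events by incidence, type and grade with no relatedness filter.

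**Conclusion.** The conflict between 11.1 and 11.3 is real and follows from the counts alone. A well-timed event with a ready alternative cause and no known pattern can only be scored *Unlikely*, whatever dechallenge and rechallenge show: 0 of 6 profiles reach *Possibly*. This assumes that the counts are applied as written and that an alternative which readily produces the event is also taken to explain it reasonably. If the second assumption fails, positive dechallenge opens *Probably*, but *Unlikely* remains met.

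The consequence is possible understatement of eltrombopag-related adverse events, and uncertainty in the rules that turn on attribution. It cannot be sized: the documents do not say how many events among up to 31 patients would fall in this cell, and 6 of 24 profiles is a count of logical cases, not a share of events. All-causality safety summaries are unaffected, and FDA reporting is not blocked by the table alone.

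**What to change.** Reconcile the two sections:

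1. State in 11.1 and 11.3 that the reasonable-possibility standard governs causality for AEs and SAEs.
2. Make the table's criteria guidance rather than mandatory counts. At the least, let plausible timing plus positive dechallenge or rechallenge qualify for *Possibly*.
3. State that *Possibly* or higher means attributable in 11.5 and associated in the FDA Reporting paragraph, and use the same cut for the related-AE summary under 2.2.
4. Use one wording for the alternative-cause criterion at every level, so that the scale is ordered.

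The cost is a text amendment and a change to the AE form. The downside is that somewhat more events will be classed as possibly related, which gives a less favourable related-AE rate and probably some additional reports.

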## 11.2 Definition of an SAE

A serious adverse event is any untoward medical occurrence that, at any dose:

a. Results in death

b. Is life-threatening

NOTE: The term "life-threatening" in the definition of "serious" refers to an event in which the subject was at risk of death at the time of the event. It does not refer to an event, which hypothetically might have caused death, if it were more severe.

c. Requires hospitalization or prolongation of existing hospitalization

NOTE: In general, hospitalization signifies that the subject has been detained (usually involving at least an overnight stay) at the hospital or emergency ward for observation and/or treatment that would not have been appropriate in the physician's office or out-patient setting. Complications that occur during hospitalization are AEs. If a complication prolongs hospitalization or fulfills any other serious criteria, the event is serious. When in doubt as to whether "hospitalization" occurred or was necessary, the AE should be considered serious. Hospitalization for elective treatment of a pre-existing condition that did not worsen from baseline is not considered an AE.

d. Results in disability/incapacity, or

NOTE: The term disability means a substantial disruption of a person's ability to conduct normal life functions. This definition is not intended to include experiences of relatively minor medical significance such as uncomplicated headache, nausea vomiting, diarrhea, influenza, and accidental trauma (e.g. sprained ankle) which may interfere or prevent everyday life functions but do not constitute a substantial disruption.

e. Is a congenital anomaly/birth defect

f. Medical or scientific judgment should be exercised in deciding whether reporting is appropriate in other situations, such as important medical events that may not be immediately life-threatening or result in death or hospitalization but may jeopardize the subject or may require medical or surgical intervention to prevent one of the other outcomes listed in the above definition. These should also be considered serious. Examples of such events are invasive or malignant cancers, intensive treatment in an emergency room or at home for allergic bronchospasm, blood dyscrasias or convulsions that do not result in hospitalization, or

Product: PROMACTA® eltrombopag  
development of drug dependency or drug abuse.

CASE4913/IRB14-147

g. All Grade 4 non-hematologic laboratory abnormalities assessed using the National Cancer Institute (NCI) Common Terminology Criteria for Adverse Events (CTCAE) v4.0. Serious hematologic AEs are not included in the definition of an SAE, as these are related to the disease and/or to the IC.

h. Serious hematologic AEs except for unprovoked arterial and venous thromboembolic events are not included in the definition of an SAE, as these are related to the disease and/or to the IC. Superficial thrombophlebitis and central line associated thrombosis will not be considered SAE.

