#### 7.5 Dose delays, modifications or discontinuation for hematologic side effects

**7.5.1 Thrombosis/Embolism:** Subjects who experience a deep venous thrombosis (excluding line-related thrombus) or a pulmonary embolus, a TIA or stroke, or a myocardial infarction at any time while on eltrombopag will discontinue the drug and go off study. Patients with platelet counts of  $> 50,000/\mu\text{l}$  at the time of thrombosis will be treated with enoxaparin or another appropriate anticoagulant as clinically indicated. They will be treated for the thrombotic event as otherwise clinically-indicated.

**7.5.2 Peripheral blood abnormalities:** The development of significant worsening of anemia or neutropenia while on study will require discontinuation of eltrombopag and additional evaluation including a bone marrow biopsy as clinically indicated.

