## 7.7 Duration of Therapy and Off Study Criteria

Depending on tolerability, eltrombopag can be administered to all assigned study subjects for a total duration of 4 weeks (counted from the first day of eltrombopag administration) unless they meet one of the following criteria for removal from the study:

1. Withdrawal of consent. The patient's desire to withdraw from the study may occur at any time. The investigator should carefully consider whether the patient's withdrawal of consent is due to an adverse event, and if so, record the adverse event as the reason for withdrawal.
2. Violation of the study protocol, including a patient's failure to return for required treatments or assessments or failure on the part of participants with reproductive potential to practice effective birth control or non-compliance.
3. At the treating physician's clinical discretion, if any specific medical or psychosocial changes in patient's condition makes them unacceptable to further participate in the study.
4. If bone marrow biopsy performed to establish remission status (around day 30-45 of remission IC), confirm refractory or persistent disease or if there is leukemic involvement of extramedullary site (biopsy confirmation of skin or organ lesions, central nervous system involvement confirmed either by cerebrospinal fluid analysis or radiological exams) at any time during study.
5. Adverse events, including intolerance of eltrombopag not resolved by dose reduction, life threatening acute hypersensitivity reaction, persistent hepatotoxicity (refer to section 7.4.2), thrombosis/embolism (DVT, PE, stroke, TIA, myocardial infarction) other than central line thrombosis (refer to section 7.5.1) or evidence of disease progression on treatment (myeloid sarcomas). Participants who are removed from the study due to adverse events will be treated and followed according to established medical practice. All pertinent information concerning the outcome of such treatment will be entered in the CRF.

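### Items g and h of the SAE definition conflict, and read literally both leave provoked thromboembolism outside SAE status although it takes the patient off study

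*Combined protocol and SAP*

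**What the plan says.** Section 11.2 lists what counts as an SAE. Item g adds Grade 4 non-hematologic laboratory abnormalities and then states: "Serious hematologic AEs are not included in the definition of an SAE, as these are related to the disease and/or to the IC". Item h returns to the subject with an exception: "Serious hematologic AEs except for unprovoked arterial and venous thromboembolic events are not included in the definition of an SAE", for the same stated reason. It then adds: "Superficial thrombophlebitis and central line associated thrombosis will not be considered SAE".

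Section 7.5 is headed "Dose delays, modifications or discontinuation for hematologic side effects". Under that heading, 7.5.1 provides that a patient on eltrombopag who has a DVT (line-related thrombus excepted), PE, TIA, stroke or myocardial infarction "will discontinue the drug and go off study". Section 7.7, item 5, repeats the criterion as "thrombosis/embolism (DVT, PE, stroke, TIA, myocardial infarction) other than central line thrombosis (refer to section 7.5.1"). Neither place separates provoked from unprovoked events.

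Section 6.3 treats thromboembolism as a safety topic for the drug. It counts DVT, PE, TIA, ischemic stroke and myocardial infarction as thromboembolic events, and names portal vein thrombosis as the most common one in the HCV studies.

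Section 11.7 ties the 24-hour report to the supplier, reports of late related events, and FDA reporting to SAE status.

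**The concern.** Three things do not fit together. Item g has no exception and item h has one, so the same unprovoked PE is outside the definition under g and inside it under h. The exception turns on *unprovoked*, a word that the protocol neither defines nor uses in its discontinuation rules, so two careful investigators could classify the same event differently. And the reason given, that such events come from the leukemia or the induction chemotherapy, settles causality in advance. Section 6.3 reports more thromboembolism on eltrombopag than on placebo, and 11.3 asks for causality to be assessed on the information available.

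At stake is prompt reporting. An event important enough to end a patient's participation may not reach the supplier within 24 hours, in a trial that lists safety among its primary goals (section 12.0).

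**Working it through.** **Side by side.** The table takes thromboembolism as hematologic, as 7.5 does and as the form of item h's exception implies.

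| Event | 11.2 item g | 11.2 item h | 7.5.1 and 7.7 item 5 |
|---|---|---|---|
| DVT (non-line), PE, TIA, stroke, MI: unprovoked | not an SAE | SAE | off study |
| The same events: provoked | not an SAE | not an SAE | off study |
| Portal vein thrombosis | not an SAE | SAE only if unprovoked | not named |
| Central line thrombosis | not an SAE | not an SAE, by name | excepted |
| Superficial thrombophlebitis | not an SAE | not an SAE, by name | not named |

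Row 1 is the contradiction between g and h. Row 2 is the gap. Line thrombosis is handled consistently and is not part of the problem.

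**Does another section close the gap?**
- 11.2 items a to d: g and h exclude *serious* hematologic events, that is, events that already meet a seriousness criterion. Meeting one does not bring them back.
- 11.4: it covers laboratory and other safety assessments, and itself excepts hematologic AEs.
- 11.5: its attribution proviso applies to progression, cytopenias and infections. Thrombosis is not listed.
- 11.7: all the expedited routes begin from an SAE. The FDA route also requires the event to be unexpected and associated with the drug, so the 24-hour supplier report is the route mainly affected.

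**Size, for illustration.** The claim rests on the text and needs no figure. For scale:
1. The plan's own safety figure (12.0) is a chance of at least 80% of seeing at least one event at 5% risk in 31 patients. 1 − 0.95^31 = 0.796, which agrees to rounding.
2. Rates in 6.3 on eltrombopag: ITP 17/446 = 3.8%; HCV 31/955 = 3.2% (placebo 5/484 = 1.0%); chronic liver disease 6/143 = 4.2% (placebo 2/145 = 1.4%). Take 3–4%, **assuming** that these rates carry over.
3. At the full 31 patients: 1 − 0.97^31 = 0.61 and 1 − 0.96^31 = 0.72. Expected number with an event: 31 × 0.03 = 0.9 to 31 × 0.04 = 1.2.
4. If the trial stops after the first stage of 12: 1 − 0.97^12 = 0.31 and 1 − 0.96^12 = 0.39.

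These are chances of any thromboembolic event. The chance of one being left out of the SAEs is smaller, by a provoked share that the documents do not give. If, as an assumption, SAE status were kept for 75%, 50% or 25% of a toxicity with a true 5% risk, the chance of seeing at least one such SAE in 31 patients would be 1 − (1 − 0.05 × share)^31 = 0.69, 0.54 or 0.32, against 0.80 with full capture.

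**The case against.** The strongest reply is that the sentence in item g follows one about laboratory abnormalities and can be read as its counterpart for blood counts. Section 11.1 uses the term in that sense, and item h then deals with thromboembolism specifically. On that reading g and h do not conflict. This is a fair reading, so it would go too far to infer that no thromboembolic event can be an SAE. But the text does not limit item g in this way, and item h still leaves provoked events out.

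Item h can also be defended as a choice: it keeps the events least explained by disease or chemotherapy. That defence needs a definition of *unprovoked*, and there is none. A reader might go further and suppose that nearly every event in hospitalised patients just after induction would count as provoked. The documents give no such figure, so the share affected is unknown.

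The events are not lost. They are collected and graded as AEs (11.7, 12.0), and for patients removed because of an AE the outcome goes into the CRF (7.7). Section 12.0 plans no SAE-rate analysis, so no planned estimate changes. An investigator might also regard stroke or myocardial infarction as non-hematologic and report it under items a to d. All of this stands, and it limits the consequence to expedited reporting.

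The rates in 6.3 come from ITP, HCV on interferon-based therapy, and chronic liver disease, with portal events prominent in the last two. Here treatment lasts up to 4 weeks and stops once an untransfused count reaches 100,000/µL, and thrombosis within the past year is an exclusion. The rates may not transfer. Nor do higher doses alone imply a higher risk: 7.2 predicts exposure at 300 mg as similar to, or by another scaling 51% above, that of HCV patients on 75 mg.

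**Conclusion.** The point holds as a defect in the reporting definition. Read literally, items g and h contradict each other on unprovoked thromboembolism and together exclude provoked thromboembolism, while 7.5.1 and 7.7 remove the patient in either case. No other section resolves this. The consequence is that such an event, though recorded as an AE, could miss the 24-hour report to the supplier and, where it would otherwise qualify, the FDA report. Sample size, the primary endpoint and the efficacy decision rule are untouched.

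The 61–72% (31–39% at 12 patients) is illustrative and assumes the 6.3 rates apply. It should not be read as the chance of an unreported SAE.

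A reader might also extend the point to every hematologic reason for stopping, since 7.5.2 says: "The development of significant worsening of anemia or neutropenia while on study will require discontinuation of eltrombopag". The documents do not support treating cytopenias in the same way: 11.5 excludes them only when they are not attributed to study medication, and item f of 11.2 gives blood dyscrasias as an example of a serious event. The finding is confined to thromboembolism.

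**What to change.** In 11.2, item g, delete the hematologic sentence or limit it expressly to blood-count abnormalities. In item h, drop *unprovoked*, so that every arterial or venous thromboembolic event meeting a seriousness criterion is an SAE. Say that this includes the events named in 7.5.1 and portal vein thrombosis, which 6.3 names and 7.5.1 does not. Keep the carve-outs for superficial thrombophlebitis and central line thrombosis.

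This changes reporting wording only; no treatment rule, endpoint or sample size changes. The cost is an amendment of two sentences and perhaps one or two additional SAE reports.
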